#### 4.5.2. Discontinuation from Protocol Participation

A subject may be discontinued from protocol participation for the following reasons:

- Subject voluntarily withdraws;
- Subject develops a medical condition that is a contraindication to continuing on study;
- The IND Sponsor or regulatory authorities stop the protocol; or,
- The IND Sponsor and/or PI assess that it is not in the best interest of the subject to continue participation or that the subject's compliance with the study is not sufficient.

# 4.6. Criteria for Pausing and Resuming the Study

The PI for each site, study team, and IND Sponsor will closely monitor and analyze study data as they become available and will make determinations regarding the presence and severity of AEs. Product administrations, new enrollments, and randomizations will be paused and the IND Sponsor will be promptly notified according to the following criteria:

- One (or more) subject experiences a Serious Adverse Event (SAE) assessed by the PI as related to study product.
- **Two** (or more) subjects experience the same **Grade 4 unsolicited AE** assessed by the PI as related to the study product.

#### Plan for Review of Pauses and Resuming Rules:

The IND Sponsor, with participation by the PSRT, will conduct the review and consult with the Data and Safety Monitoring Board (DSMB) to make the decision to resume, amend or close the study. As part of the pause review, the reviewers will also advise on whether the study needs to be paused again for any subsequent AEs of the same type.

Product administrations, new enrollments, and randomizations would resume only if review of the AEs that caused the pause result in a recommendation to permit further product administrations, enrollments, and randomizations. When indicated, safety data reports and changes in study status will be submitted to relevant regulatory authorities including the site IRB/EC in accordance with Section 5.5 and site institutional policy.

# 5. SAFETY AND ADVERSE EVENTS

# 5.1. Adverse Events

An adverse event (AE) is any untoward or unfavorable medical occurrence in a human subject, including any abnormal sign (e.g., abnormal physical exam or laboratory finding), symptom, or disease temporally associated with the use of study treatment, whether or not considered related to the study treatment. AEs will be graded according to the Table for Grading Severity of AEs (Appendix IV).

All AEs will be followed until they have resolved or are considered stable during the course of the study. If the event has a resolution date, this date must be recorded on the Adverse Event form, regardless of whether or not it falls within the AE reporting period.

# 5.1.1. AE Reporting Period

The following guidelines will be used to determine if an AE should be recorded in the database:

- Solicited AEs (i.e. reactogenicity parameters) will be recorded in the study database for 7 days after each product administration without the collection of their relationship to study product.
- Unsolicited AEs and their relationship to study product must be recorded in the study database immediately after the first product administration at Visit 02 through the one month visit that follows the last product administration. Therefore, the following rules apply:
  - If a subject receives all 3 study product administrations, then the AE Reporting Period for unsolicited AEs and their relationship to study product is immediately after Visit 02 through Visit 05.
  - If a subject only receives the first product administration at Visit 02 but not the second or third, then the AE Reporting Period for unsolicited AEs and their relationship to study product is immediately after Visit 02 through Visit 03.
  - If a subject receives the first and second product administrations at Visit 02 and Visit 03, respectively, but not the third, then the AE Reporting Period for unsolicited AEs and their relationship to study product is immediately after Visit 02 through Visit 04.
- Only SAEs (as defined in Section 5.2), new chronic medical conditions, and confirmed cases of DENV infection, diagnosed locally or by the PDL, are recorded as AEs through the last study visit.
- Confirmed cases of ZIKV infection are not recorded as an AE unless the infection meets the definition of a SAE. ZIKV infections must be recorded on the ZIKV Endpoints Form throughout the full duration of the study.

# 5.2. Serious Adverse Events

# 5.2.1. Serious Adverse Event Definition

The term "serious adverse event" (SAE) as defined in US 21 Code of Federal Regulations (CFR) 312.32 as follows: "an adverse event or suspected adverse reaction is considered "serious" if, in the view of either the investigator or sponsor, it results in any of the following outcomes: Death, a life-threatening adverse event, inpatient hospitalization or prolongation of existing hospitalization, a persistent or significant incapacity or substantial disruption of the ability to conduct normal life functions, or a congenital anomaly/birth defect. Important medical events that may not result in death, be life-threatening, or require hospitalization may be considered serious when, based upon appropriate medical judgment, they may jeopardize the patient or subject and may require medical or surgical intervention to prevent one of the outcomes listed in this definition. Examples of such medical events include allergic bronchospasm requiring intensive treatment in an emergency room or at home, blood dyscrasias or convulsions that do not result in inpatient hospitalization, or the development of drug dependency or drug abuse."

"Life threatening" refers to an AE that, at occurrence, represented an immediate risk of death to the subject. An event that hypothetically may cause death if it occurs in a more severe form is not considered life-threatening. Similarly, a hospital admission for an elective procedure is not considered a SAE.

# 5.2.2. Reporting Serious Adverse Events to the IND Sponsor

AEs that meet the definition of a SAE must be reported from the time that the subject signs the informed consent/assent form through the last study visit by the study site and submitted on an expedited basis to the IND Sponsor, according to sponsor guidelines as follows:

- results in death;
- is life-threatening;
- results in persistent or significant disability/incapacity;
- requires unplanned inpatient hospitalization or prolongation of existing hospitalization;
- is a congenital anomaly/birth defect in the offspring of a study subject; or,
- is an important medical event that may jeopardize the subject or may require intervention to prevent one of the other outcomes listed above.

Additionally, any event, regardless of severity, which in the judgment of a site PI represents a SAE, may be reported on an expedited basis.

**Reporting to the IND Sponsor**: Within 3 calendar days of site awareness of the SAE occurrence, the site PI or designee will communicate an initial SAE report to the IND Sponsor through the communication methods provided by VRC's CRO. The site will remove personal identifying information about the subject from SAE case reports before submission to the IND Sponsor.

Any SAE entered into the study database will generate an automatic email notification to the IND Sponsor. A written event summary by the study site should be sent to the IND Sponsor within 7 calendar days and sooner, if possible, in case of death. Additional information should

be submitted as it becomes available. The IND Sponsor will use this information to comply with FDA regulations mandating notification of expedited SAEs.

# 5.2.3. IND Sponsor Reporting to the FDA

It is the responsibility of the IND Sponsor to make the determination of which SAEs are "serious and unexpected suspected adverse reactions" (SUSARs) as defined in 21 CFR 312.32.

- *Suspected adverse reaction* means any AE for which there is a reasonable possibility that the drug caused the AE.
- *Unexpected adverse event* means an AE that is not listed in the IB or is not listed at the specificity or severity that has been observed.

All SUSARs, as determined by the IND Sponsor, will be reported to the FDA as IND Safety Reports. All IND Safety Reports will be provided to all participating site PIs by the IND Sponsor and should be submitted to site local or national regulatory authorities as required.

The IND Sponsor will also submit an IND Annual Report of the progress of the investigation to the FDA as defined in US 21 CFR 312.33.

#### 5.2.4. Serious Adverse Event Reporting to the Data and Safety Monitoring Board

SAEs that occur during the study will be reported to the DSMB by the IND Sponsor or sponsor representative on a monthly basis. However, any SAE that is reported to the FDA as a IND Safety Report will be reported to the DSMB as soon as possible.

#### 5.2.5. Serious Adverse Event Reporting to the Institutional Biosafety Committee

In keeping with Institutional Biosafety Committee (IBC) requirements, sites will follow their IBC reporting regulations per institutional policy.

# **5.3. Protocol Deviation**

A Protocol Deviation is defined as any change, divergence, or departure from the IRB/ECapproved study procedures in a research protocol. This includes but is not limited to:

- Those that occur because a member of the research team deviates from the protocol.
- Those that are identified before they occur, but cannot be prevented.
- Those that are discovered after they occur.

# 5.4. Unanticipated Problem

A serious Unanticipated Problem (UP) is defined as any incident, experience, or outcome that meets all three of the following criteria:

- unexpected in nature, severity, or frequency in relation to the research risks that are described in the protocol, informed consent, IB, other study documents or in consideration of the characteristics of the subject population being studied; **and**
- related to participation in the research; **and**

• suggests that the research places subjects or others at a greater risk of harm (including physical, psychological, economic, or social harm) than was previously known or recognized.

Non-serious UP: An UP that is not an Adverse Event (UPnonAE) is an unanticipated problem that does not fit the definition of an AE, but which may, in the opinion of the investigator, involve risk to the subject, affect others in the research study, or significantly impact the integrity of research data. Such events would be considered a non-serious UP. For example, we will report occurrences of breaches of confidentiality, accidental destruction of study records or samples, or unaccounted-for study drug.

# 5.5. Reporting to Site IRBs/ECs and Relevant Regulatory Agencies

Each site PI is responsible for reporting study information to the site IRB/EC per the IRB/EC requirements for reporting and to other relevant regulatory authorities in accordance with their institutional and country requirements for reporting.

Site-specific data reports will be made available through the data management CRO to facilitate expedited and continuing review reporting requirements.

Only the IND Sponsor will submit reports to the FDA. Any IND Safety Report that is submitted to the FDA will also be provided to all sites, with instructions on whether or not any action needs to be taken. Investigators must maintain documentation of compliance with actions required for IND Safety Reports.

# 5.6. Data and Safety Monitoring Board

The PSRT (Section 8.9.1) will have the primary responsibility for the regularly scheduled oversight of safety data and SAE reviews. The NIAID DSMB will review cumulative study data at least twice per year or as often as recommended by the DSMB to evaluate safety, study conduct, and scientific validity and integrity of the trial and will be consulted if there is a study pause as required by Section 4.6.

The DSMB members will assess the timeliness, completeness, and accuracy of the data submitted to them for review and whether the data are sufficient for evaluation of the safety and welfare of study subjects. The DSMB Executive Secretary will be provided with a sealed copy of the randomization codes needed for the DSMB review of the safety data. The DSMB will also assess the performance of overall study operations and any other relevant issues, as necessary. Following each review, the DSMB will provide its recommendations to the IND Sponsor, including whether the study should continue without change, be modified, or be terminated.

In addition, SAEs will be reported to the DSMB as outlined in Section 5.2.4.

# 6. STATISTICAL CONSIDERATIONS AND SAMPLE ANALYSIS

# 6.1. Overview

This is a multicenter, randomized, study to evaluate the safety, immunogenicity, and efficacy of VRC-ZKADNA90-00-VP (ZIKVwt DNA vaccine) or placebo. The hypotheses are that the ZIKVwt DNA vaccine will be safe and will elicit a ZIKV-specific immune response. In **Part A**, the primary objective is to evaluate the safety and tolerability of the vaccine. In **Part B**, the primary objectives are to evaluate the safety, tolerability, and efficacy of the vaccine compared to placebo. In **Part A** and **Part B**, secondary and exploratory objectives relate to immunogenicity/durability of immune responses, incidence of subclinical and symptomatic ZIKV infection, and ZIKV viremia/viruria following infection.

# 6.2. Endpoints

# 6.2.1. Safety

Assessment of product safety will include clinical observation and monitoring of hematological and chemical parameters. Reactogenicity will be closely monitored for 7 days after each product administration and safety evaluated by clinical visits through the study duration of 32 or 96 weeks in **Part A** or **Part B**, respectively.

The following parameters will be assessed:

- Local reactogenicity signs and symptoms;
- Systemic reactogenicity signs and symptoms;
- Laboratory measures of safety;
- Adverse events;
- Serious adverse events, new chronic medical conditions, and confirmed cases of DENV; and,
- ZIKV infection events (**Part B only**).

# 6.2.2. Immunogenicity

The principal immunogenicity endpoints are 4 weeks after the last product administration compared to Day 0 as measured by neutralization assay. Exploratory immunogenicity endpoints are measured by neutralization assay, ELISA, and other research tests as described in Section 1.7.

# 6.2.3. Efficacy (Part B only)

The primary efficacy endpoint is the ZIKV incidence defined as virologically confirmed infection by PCR virus detection. The secondary efficacy endpoint is the incidence of subclinical virologic cases.

# 6.3. Sample Size and Accrual

# 6.3.1. Sample Size Considerations: Part A

**Part A** of the study targets healthy adults (age 18-35). Since the risk of GBS has been shown to increase with age, the study population excludes those who might be at higher perceived risk for GBS [54-56]. Ninety subjects will be randomized 1:1:1 to three vaccination arms. The sample size decision is based on the evaluation of vaccine safety and immunogenicity. Accrual up to 100 subjects is permitted if additional subjects are needed for safety and immunogenicity evaluations.

# 6.3.1.1. Power Calculations for Evaluation of Safety

The ability of the study to identify safety events can be expressed in terms of the probability of observing one or more event of interest (e.g., AEs) within each group assuming a range of underlying true event rates. With 30 subjects per group, assuming the true event rate of 0.3%, there is a probability of 8.6% to observe at least one event and a probability of 0.4% to observe more than one event (Table 2).

True Event Rate (%)	Pr (0 event) (%)	Pr (more than one event) (%)
0.1	97.0	<0.1
0.3	91.4	0.4
0.5	86.0	1.0
1.0	74.0	3.6
3.0	40.1	22.7
5.0	21.5	44.6

 Table 2:
 Probability of Observing Safety Events within a Group (n=30)

Table 3 shows the 95% confidence intervals (CIs) of the true event rate based on the observed safety data. Calculations are done using exact binomial test. For a given arm with sample size n=30, if none of the subjects experience a safety event, the 95% CI has upper bound as 0.116.

# Table 3:Two sided 95% CIs Based on Observed Rates of Safety Endpoints within a
Group (n=30)

Observed	95% CI		
event rate	Lower bound	Upper bound	
0/30	0	0.116	
1/30	0.001	0.172	
2/30	0.008	0.221	
3/30	0.021	0.265	
4/30	0.038	0.307	
5/30	0.056	0.347	

# 6.3.1.2. Power Calculations for Evaluation of Immunogenicity

The evaluation of immunogenicity includes the magnitude of the immune response as well as the positive response rate. The primary endpoint is the immune response measured by neutralization assay at 4 weeks after the last product administration. Table 2 provides the probability of observing zero or more than one positive responses within a group of size 30 and Table 3 provides the 95% CIs of the positive response rate in the vaccinated population. Neutralization assay data are close to being log-normally distribution. The magnitude of immune response due to the study vaccine can be evaluated by the fold change from baseline. Table 4 shows the power of detecting a range of fold changes, assuming normal distribution after log transformation with standard deviation=1, within a group of size 30. Table 5 presents the power of detecting between-arm differences over a range of effect sizes, assuming normal distribution after log transformation with common standard deviation. The calculations are done using t-tests in log scales. With 30 subjects per group, the study is capable of detecting with over 80% power the fold change of 0.75 and above within a group, and over 80% power the between-arm difference of 0.80 standard deviation and above in log scale.

Table 4:	Power of Detecting a	Range of Fold	Changes from	Baseline Imm	une Response
	Tower of Dettering a	Range of Lora	Changes nom	Daschine Innin	une response

Fold change	Power (%)
0.25	22
0.50	57
0.75	84
1.00	96

Table 4 is based on assuming normal distribution after natural log transformation with standard deviation=1, by one sample two-sided t-test with type I error rate of 5%, within a group (n=30).

Table 5:	Power of Detecting	Between-Arm	Difference over a	Range of	Effect Sizes
----------	---------------------------	-------------	-------------------	----------	---------------------

Effect size of between-arm difference	Power (%)
0.5	48
0.6	63
0.7	76
0.8	86
0.9	93

Table 5 is based on assuming normal distribution after log transformation, by two-sample two-sided t-test with type I error rate of 5% (n=30).

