#### 3.2.1. Study Definitions and Derived Variables

The baseline value will be defined as the last value obtained prior to the receipt of the first product administration on Day 0 (Visit 02).

Individual neutralization antibody (NAb) assay results will be reported as a titer. Fold-rise (NAb) is a measure that describes how much the NAb titer changes from an initial to a final value. The fold-rise is calculated as the ratio of the final value to the initial value. Subjects will be tested for baseline ZIKV serostatus based on serum samples collected at screening, Visit 01.

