#### 9. IMMUNOGENICITY EVALUATION

The principal immunogenicity endpoints are measured at Day 0 (Visit 02) and 4 weeks after the third administration (Visit 05) by NAb. We assume NAb results will follow a log-normal distribution.

The following summaries will be presented by study group and study visit separately for Part A and Part B for all subjects in each of the ITT, PP and mITT analysis populations. Summaries are presented over all subjects and stratified by baseline ZIKV serostatus.

- The number and percentage of subjects with positive NAb response, defined as a titer≥30, along with their exact 95% CIs and p-values from a Chi-squared test comparing study groups. (Table 19 through Table 24, Appendix 1)
- GMTs and their CIs, p-values from a t-test comparing log-NAb titers between study groups. (Table 25 through Table 30, Appendix 1)
- Geometric mean fold rise (GMFR) in NAb from baseline with the corresponding confidence interval and (1) p-value from a paired t-test comparing the log-NAb titers between baseline and post-administration within each treatment arm, and (2) p-value from t-test comparing log-transformed fold increases in NAb between study groups. Non-parametric tests will be considered if the normality assumption is not realized. (Table 25 through Table 30, Appendix 1)
- Boxplots of NAb titers. (Figure 15 through Figure 26, Appendix 2)
- Reverse cumulative distribution curves of NAb titers. (Figure 3 through Figure 14, Appendix 2)

Exploratory analysis of NAb for other visits will be presented in a similar fashion as data are available.

A listing of individual NAb titer levels, whether positive and the corresponding planned and actual collection dates are presented in Listing 16 - Listing 17, **Appendix 3.** For any immunogenicity reports released prior to database lock and study unblinding, a coded subject identifier will be included in listings to prevent unblinding any subject's study product assignment.

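### Table 4 in Protocol 6.3.1.2 labels the ratio minus 1 as fold change, so the stated within-group detectable effect of 0.75 should read 1.75

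*Combined protocol and SAP*

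**What the plan says.** Protocol 6.3.1.2 chooses its effect measure for Part A immunogenicity as follows: "The magnitude of immune response due to the study vaccine can be evaluated by the fold change from baseline". It gives no formula for fold change. Table 4 lists fold changes of 0.25, 0.50, 0.75 and 1.00 with power of 22%, 57%, 84% and 96%. The text draws the conclusion: "the study is capable of detecting with over 80% power the fold change of 0.75 and above within a group".

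The assumptions are stated in full. The note to the table says "Table 4 is based on assuming normal distribution after natural log transformation with standard deviation=1" and "by one sample two-sided t-test with type I error rate of 5%, within a group (n=30"). The text adds: "The calculations are done using t-tests in log scales".

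The SAP takes its sample-size section from Protocol 6.3 by reference (SAP section 5). In SAP 3.2.1 it defines the quantity that will be analysed: "The fold-rise is calculated as the ratio of the final value to the initial value". SAP section 9 reports the geometric mean fold rise and, within each arm, a "p-value from a paired t-test comparing the log-NAb titers between baseline and post-administration within each treatment arm". A paired t-test on log titers is a one-sample t-test on the log of that ratio, which is the test Table 4 powers.

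**The concern.** On a ratio scale the null value is 1. A fold change below 1 is a fall in titer, and a fold change of exactly 1 is no change. Table 4 nevertheless shows 84% power at 0.75 and 96% power at 1.00, and the sentence in the text claims over 80% power across a range that includes 1.00, the null itself. Either the powers or the labels must be wrong.

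This is the only within-group detectable effect stated for Part A immunogenicity, and Protocol 6.3.1 says the Part A sample size rests on safety and immunogenicity together. A reader who sets a reported geometric mean fold rise against Table 4 would be off by exactly 1 on every row.

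**Working it through.** **Inputs**, all from Protocol 6.3.1.2: n = 30; one-sample two-sided t-test; type I error 5%; SD = 1 on the natural log scale. The SAP also uses natural logs throughout (SAP 6.1).

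**Formula.** With effect δ on the log scale, the noncentrality is λ = δ√30 / 1 = 5.477 δ, with 29 degrees of freedom. Power = P(T > t₀.₉₇₅,₂₉) + P(T < −t₀.₉₇₅,₂₉), where T is noncentral t with parameter λ.

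**Step 1: reproduce Table 4.** Each way of turning the printed value x into δ was tried in turn:

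| Printed x | Printed power | δ = ln(1 + x) | δ = ln(x), x as ratio | δ = x on the log scale |
|---|---|---|---|---|
| 0.25 | 22% | 21.9% | about 100% | 26.3% |
| 0.50 | 57% | 57.4% | 95.6% | 75.4% |
| 0.75 | 84% | 84.2% | 33.2% | 97.8% |
| 1.00 | 96% | 95.6% | 5.0% | 99.96% |

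Only δ = ln(1 + x) matches all four rows to rounding. For the third row, δ = ln(1.75) = 0.5596 and λ = 0.5596 × 5.477 = 3.07, giving 84.2%. Base-10 and base-2 logs, one-sided tests, an SD of √2 and a two-sample test were also tried, and none reproduces the full table. A normal approximation with δ = ln(1 + x) gives 23.0%, 60.3%, 86.6% and 96.7%, which points to the same reading but fits less well.

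**Step 2: express the rows as ratios.** If δ = ln(1 + x), the final-to-initial ratio is 1 + x. The rows are therefore 1.25, 1.50, 1.75 and 2.00, and the printed column is the ratio minus 1.

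**Step 3: find the 80% threshold.** Solving for power = 80% gives δ = 0.529, so the ratio is e^0.529 ≈ 1.70. The claim of over 80% power therefore holds at 1.75 and above on the ratio scale.

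**Step 4: read the printed values literally under SAP 3.2.1.** A ratio of 0.75 is a 25% fall, |δ| = 0.2877, power 33.2%. A ratio of 1.00 gives δ = 0 and a rejection probability of 5.0%, the type I error. Under this reading the first two rows would have more power than printed (about 100% and 95.6%), and power would fall down the column instead of rising.

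**Step 5: check the neighbouring table.** The between-arm powers in Table 5 reproduce as printed (47.8%, 62.8%, 76.0%, 86.1% and 92.9% for standardised differences of 0.5 to 0.9). The problem is confined to Table 4 and the sentence that repeats it.

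**The case against.** The best defence is that nothing was miscalculated. All four powers are correct under one consistent reading, in which fold change means the proportional increase, (final − initial) / initial. The protocol says fold change and the SAP defines fold-rise, so the ratio definition belongs to a different term in a different document. Power also climbs steadily towards 1.00, so a statistician would soon see that a ratio cannot be meant. The 33% and 5% figures measure the size of the labelling discrepancy; they are not a power shortfall in the trial.

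Much of this stands. The percentages are right, 30 per group is unaffected, immunogenicity is a secondary objective in Part A, and the planned analysis does not use Table 4. Protocol 1.4 also reports that Part A vaccinations ended in October 2017, and Protocol 1.5 that the Part B regimen had been chosen, so no design decision is reopened.

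The defence does not rescue the label. The proportional-increase meaning appears nowhere in the text. The only definition in the documents is a ratio, the SAP adopts the protocol's sample-size section without comment, and it runs the same within-arm test on the ratio scale. That a careful reader can work out the intended meaning does not make the printed sentence correct.

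**Conclusion.** The concern holds. Under the SAP's definition, the stated within-group detectable effect is wrong by exactly 1 on the fold-change scale: 0.75 should be 1.75, and the Table 4 rows should be 1.25, 1.50, 1.75 and 2.00. The powers of 22%, 57%, 84% and 96% are correct for those ratios.

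This rests on the protocol's own assumptions, with SD 1 taken as the SD of the log ratio from baseline (the reading that reproduces the table), and on fold change in the protocol meaning the same quantity as fold-rise in the SAP. If the authors meant proportional increase, the numbers stand and what is missing is the definition. Either way it is a minor correction with no effect on sample size, conduct or analysis.

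**What to change.** In Protocol 6.3.1.2, relabel the Table 4 rows 1.25, 1.50, 1.75 and 2.00, leave the powers as they are, and change the sentence to state over 80% power for a 1.75-fold rise and above within a group. A short statement that fold change is the ratio of the post-administration value to the baseline value, as in SAP 3.2.1, would tie the two documents together.

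An equally sound alternative is to keep the printed values, head the column as proportional increase (fold change minus 1), and reword the sentence to match.

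The cost is four labels and one sentence. Because SAP section 5 refers to Protocol 6.3, it needs no separate edit.
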